Angiogenesis plays a fundamental role in tumor growth and metastasis. Investigations by Teruyama et al. and Mastuyugin et al. have established a relationship between VEGF expression and p450 aromatase activity (Teruyama, 2001; Mastuyugin, 2002). We have previously shown that dynamic contrast enhanced MRI in conjunction with compartmental modeling may be used to assess the angiogenic status of tumors while enabling the study of both breasts (Su, 2002). Additionally, image based measurement techniques do not suffer from the errors due to tissue heterogeneity and use of limited spatial sampling imposed in methods such as histology. Furthermore, MRI based parameters that describe breast physiology have been found to correlate well with immunohistochemically measured angiogenesis markers (Su, 1995; Su, 1994; Su, 1996). *Thus, dynamic contrast enhanced MRI will be used as a secondary surrogate marker in the proposed study.*

Methodology to test the hypothesis: Core biopsies will be obtained from patients whose mammographic findings are suspicious for DCIS. Patient will undergo MRI study prior the biopsy. At the time of biopsy, a portion of the tissue retrieved will be sent in formalin for histopathological examination for Ki-67, ER, PR and angiogenesis markers evaluation.

1 mg of anastrozole administered orally daily for 4 weeks after the diagnosis of DCIS/invasive breast cancer. The reason for using a 4-week regimen is that this is the average time between diagnostic biopsy and definitive lumpectomy or mastectomy.

Patients will undergo MRI at baseline before therapy and then again after anastrozole treatment that will be followed immediately by definitive surgical procedure, i.e. lumpectomy or mastectomy. Lumpectomy/mastectomy specimen will be again evaluated for the level of tumor

Ki-67 decline and the level of angiogenesis markers. The specimen will be subjected to the routine histopathological, and ER and PR evaluation. Histopathological changes pre and post anastrozole will be evaluated in an exploratory analysis.

Detailed Methodology

1. **Quantification of Ki-67 as a Primary Marker to Monitor Response to Chemoprevention by Aromatase Inhibitor Anastrozole**

Measurement of Ki-67 Levels.

[figure not shown]
Measurement of **Ki67** will be performed with the MIB1 mouse monoclonal antibody. To ensure acceptable precision, quantitation of Ki67 will involve the counting of 1000 cells.

Other Tissue Biomarkers.

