the two parameters V_b and K_2 obtained from the kinetics of Gd-DTPA will be calculated. For each parameter, the values from all pixels will be sorted in a descending order, then the cut-off values of the top 90% pixels, 80% pixels, 10% pixels will be determined to generate the pixel population distribution curve. In addition to the full spectrum of the population, each data point in the population distribution curve (representing a subgroup of pixels from a tumor) can also be separately used in the correlation analysis. As demonstrated in a previous study, the out-flux transport rate K_2 could be related to the vascular permeability and was correlated well with the aggressive growth of tumors, but the relationship can only be revealed from the top half pixel population where the blood supply was sufficient, not in entire pixel population. Therefore, the unique analysis of pixel population distribution curve allows the analysis in a certain subgroup of interest. With the full population spectrum available, the problems associated with the limit of the pharmacokinetic analysis and the problem of tumor heterogeneity can be handled properly. We will use the 50% pixel population of the parameter in each tumor.

3. **Immunohistochemistry of p53, TSP-1, CD31, CD105, and VEGF as Exploratory Markers of Angiogenesis in neoadjuvant setting.** We reported recently that mutant p53 (mp53) was associated with decreased expression of an endogenous inhibitor of angiogenesis, thrombospondin-1 (TSP-1), and increased microvessel density in breast cancer. Carcinoma-specific levels of p53, TSP-1, and tumor angiogenesis were determined using semiquantitative immunohistochemistry (IHC) methods. Acquisition of mp53 was significantly associated with decreased TSP-1 and increased angiogenesis. An angiogenesis index integrating mp53, TSP-1, and angiogenesis (CD31) scores was found to be an independent predictor of survival in univariate and multivariate analyses that included lymph node status. We have also shown increased angiogenesis is associated with increased VEGF.

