Biotechnology, Santa Cruz, CA); TSP-1 was detected with clone p12 (Immunotech, Marseille, France), and CD31 was detected with clone JC/70A (Dako, Carpinteria, CA). Paraffin-embedded MCF-7 40F and MCF-7 wt breast cancer cells were used as positive controls for p53 and TSP-1 IHC staining, respectively. Titrations were performed for all antibody reagents to insure minimal background staining and optimal antigen detection. Invasive breast carcinoma specimens that stained negative for p53 or TSP-1 were used as negative controls. Entire tissue sections were evaluated for intensity and percentage of tumor cells staining positively. Only the malignant component was scored for each case. The intensity of p53 staining was scored as follows: negative when <5% of tumor cells displayed staining; 1+ when intensity was mild; 2+, moderate; 3+, when intensity was equal to the positive control; and 4+ when intensity was greater than the positive control. The 5% cutoff used to delineate a positive staining result was based on the previously published cutoff values by Grant *et al.* in melanoma, and Poller *et al.* in mammary ductal carcinoma *in situ* and on observations that tumors showing only weak focal p53 protein expression had expression of p53 equivalent to that sometimes seen in normal cutaneous basal cells. HScores were assigned on the basis of multiplying the percentage of cells staining positive by the intensity of staining plus 1 [HScore = % positive x (intensity + 1)]. HScores are an objective measurement of tumor heterogeneity reflecting the variability in percentage and intensity of staining within a tumor and provide a single unit of measure for the amount of marker present in the field examined, as originally described in early work to quantitate estrogen receptor content in breast cancer by IHC (Mehta, 2001). All procedures will be performed by pathologists who had no previous knowledge of the clinical outcomes for this series of cases.

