Angiogenesis controls with intermediate vessel counts will be run in parallel with each series of slides to insure appropriate CD31 staining. An invasive breast carcinoma specimen with high microvascular staining will be used for the positive control, and the nonstaining areas in the same tumor tissue will be used for the negative control. Light microscopy will be used to identify three regions within or immediately adjacent to the tumor that contained the greatest microvessel density ("hotspots"). Microvessel counts were then performed using a x200 field within the designated hotspot. Of the three areas where the highest number of discreet microvessels are stained, the area of greatest counts will be chosen for scoring. Any immunoreactive endothelial cell that is separate from adjacent microvessels is considered a "countable" vessel.

Image Analysis.

On the basis of the intracellular and extracellular localizations of TSP-1, tumor expression levels of TSP-1 were measured by image analysis as described previously to integrate overall tissue expression levels. Briefly, we used a CAS 2000 two-color system (Becton Dickinson, San Jose, CA) that used a light microscope attached to an interactive microcomputer capable of high-speed digital image processing for cell measurements. Image channels were matched to two-component immunohistochemical staining to enhance the image of one stain in each channel. One channel was used to identify all components in the tissue counterstained with methyl green (*i.e.*, all nuclear components), and the other channel was used to calculate the density of brown stain (diaminobenzidine) per tissue area to identify the proportion of cells stained with antibodies to TSP-1. Image analysis-based units of staining are reported as absorbance (*A*). A negative control

accompanying each specimen was used to set the antibody threshold such that nonspecific background staining was eliminated from the study measurement. A minimum of 10 fields with varying intensities were examined for all radical prostatectomy, transurethral prostatectomy, or biopsy specimens.

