11.0 STATISTICAL CONSIDERATIONS

Statistical Power: In this non-randomized trial, the primary surrogate marker will be Ki-67. Individuals who exhibit at least 40% reduction in Ki-67 from baseline will be categorized as responders. For p = probability of response, the null hypothesis is specified as p_0 , and the alternative as p_1 . Our null hypothesis is that after 4 weeks of therapy, no more than 5% of the subjects will exhibit at least 40% decrease in Ki-67 levels. Table 1 gives the number of subjects necessary to detect differences of 25% to 45% from the null proportion of 5%, using the binomial test with a significance level of 0.05. Thus, for 90% power, 24 evaluable subjects are necessary to detect a difference of 25% from the null. Because of the necessity of working with patients with a small tumor size all patients accrued may not be evaluable. We anticipate a non-evaluability rate of 50% as quoted by experienced investigators. Hence, we will accrue 42 patients on this trial.

In this non-randomized trial, the primary surrogate marker will be Ki-67 level.

Table 1. Number of subjects, $p_0 = 0.05$

p_1	80% Power	90% Power
0.30	18	24
0.35	12	18
0.40	10	12
0.45	9	10
0.50	5	9

All of the quantitative results generated by IHC (percentage of eg. Ki67) will be given as their arithmetic mean levels. The comparison of changes in proliferation markers and receptor levels between responders and nonresponders will be performed using the Mann-Whitney U test.

The Primary outcome is response to treatment. For each participant, the post-treatment level of Ki-67 will be compared to the pre-treatment level of ki-67. If at least a 40%

decrease from the pretreatment level achieved, the participant will be classified as a responder. The proportion responding and the 95% confidence interval for this proportion will be calculated. The 2-sided binomial test with $\alpha = 0.05$ will be performed to test $p_0 = 0.05$ vs. $p_0 \neq 0.05$.

The secondary aims of the study are to evaluate change from baseline in the MRI parameters, vascular volume (V_b) and K_2 . The distribution in changes from baseline in tumor estrogen, V_b , and K_2 will be examined using probability plots. The Kolmogorov-Smirnov goodness-of-fit test for normality will be performed. If indicated, normalizing transformations will be applied. Ninety-five percent confidence intervals for mean change from baseline and mean percent change from baseline will be computed.

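### The Ki-67 reading behind the primary endpoint has no rule for choosing cells, pairing the staining or masking the reader, so in this single-arm trial any reading shift counts as drug effect

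*Combined protocol and SAP*

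**What the plan says.** Section 2.0, Detailed Methodology, item 1, covers the Ki-67 measurement. It names the MIB1 antibody and adds: "To ensure acceptable precision, quantitation of Ki67 will involve the counting of 1000 cells". It does not say who reads, how many readers there are, how the counted cells are selected, when slides are stained, or what the reader knows. The next paragraph of that section requires ten randomly chosen high-power fields, but only for the other analytes.

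The one masking statement for tissue reading is in item 3, which is headed "Immunohistochemistry of p53, TSP-1, CD31, CD105, and VEGF as Exploratory Markers of Angiogenesis in neoadjuvant setting". It reads: "All procedures will be performed by pathologists who had no previous knowledge of the clinical outcomes for this series of cases". Automated measurement is described in that item too, for one marker only: "tumor expression levels of TSP-1 were measured by image analysis as described previously".

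Section 9.0 places the first Ki-67 value on the core biopsy and the second after lumpectomy. Section 11.0 sets the design and endpoint: "In this non-randomized trial, the primary surrogate marker will be Ki-67", and "Individuals who exhibit at least 40% reduction in Ki-67 from baseline will be categorized as responders". Under the null hypothesis, "no more than 5% of the subjects will exhibit at least 40% decrease in Ki-67 levels". The test is a two-sided binomial test at 0.05, with 24 evaluable patients for 90% power against a 30% response rate.

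**The concern.** The primary endpoint is itself a comparison of two slide readings, so masking to clinical outcome does not protect it, even if that sentence is taken to reach Ki-67. What would protect it is that the reader does not know which slide is post-treatment or what the same patient's other value was, and that the two sections are stained under the same conditions. The plan asks for none of these. Followed as written, it allows a reader who knows the baseline value to choose the cells to count on the post-treatment slide, and it allows core and excision to be stained in different runs.

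A control arm would carry the same shift and cancel it, but this trial has none. Baseline is always the core and follow-up is always the excision, so a systematic difference between the two readings falls on the treatment contrast. The null of 5% is low and fixed, and a small rise in chance responders uses up much of the error allowance. Counting 1000 cells limits sampling error; it does nothing about a shift in one direction. The other Ki-67 summaries in Section 10.1 (absolute change and the share below 10%) rest on the same readings.

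**Working it through.** **1. The plan's own figure.** Inputs from Section 11.0: p0 = 0.05, p1 = 0.30, n = 24, two-sided 0.05. The exact binomial test with 0.025 in the upper tail rejects at 5 or more responders. P(X ≥ 5 | 24, 0.05) = 0.0060, and the power P(X ≥ 5 | 24, 0.30) = 0.889. The stated 24 for 90% power is reproduced to within about a point of power. If the two-sided p-value is instead built by the minimum-likelihood method, rejection starts at 4 responders, with error 0.0298 and power 0.958. The plan does not say which applies; I use the stricter rule, at least 5 of 24.

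**2. Sensitivity to the chance response rate.** Suppose the drug does nothing and reading conditions lift the chance of a recorded 40% fall from 5% to 10%. The false-positive rate then goes from 0.6% to 8.5% (at least 5 of 24), or from 3.0% to 21.4% (at least 4 of 24).

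**3. How a reading shift moves the chance rate.** Assume no true change, a log ratio of post to pre that is normal with a given SD, and a uniform relative undercount b of post-treatment slides. The chance of a recorded fall of at least 40% is

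p = Φ((ln 0.6 − ln(1 − b)) / SD).

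For SD 0.3 and b = 0: p = Φ(−0.511 / 0.3) = Φ(−1.703) = 4.4%. For b = 0.10: p = Φ((−0.511 + 0.105) / 0.3) = Φ(−1.352) = 8.8%. The SD and b are assumptions; the documents give neither.

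P(X ≥ 5 of 24), with p in brackets:

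| SD | b = 0 | b = 5% | b = 10% |
|---|---|---|---|
| 0.25 | <0.1% (2.0%) | 0.1% (3.3%) | 0.7% (5.2%) |
| 0.3 | 0.4% (4.4%) | 1.5% (6.3%) | 5.5% (8.8%) |
| 0.4 | 8.7% (10.1%) | 17.4% (12.5%) | 31.3% (15.5%) |
| 0.5 | 30.4% (15.4%) | 43.4% (17.9%) | 58.2% (20.9%) |

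**4. Cross-check by simulation.** Pairs of 1000-cell counts were simulated with no true change and an assumed baseline Ki-67 of 10%. Counting error alone gives a 40% fall in 0.01% of pairs (0.6% at a baseline of 5%), so the 1000-cell rule does its own job. With an assumed 20% CV per reading, the chance rate is 5.2%; with a 10% undercount of post slides it is 10.0%. P(X ≥ 5 of 24) goes from 0.7% to 8.5%. This matches the SD 0.3 row: the log-ratio SD from a 20% CV is √2 × √ln(1.04) = 0.28, and counting error at 10% adds about √2 × √(0.9/100) = 0.13, for a total of √(0.28² + 0.13²) = 0.31.

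**5. What the table separates.** Reading across a row shows the effect of a reading shift, which masking and same-run staining can reduce. Reading down the first column shows the effect of measurement noise alone against a 5% null, which they do not fix.

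**The case against.** **The documents are silent; they do not say that readers are unmasked.** This is correct. The masking sentence closes the exploratory-marker subsection, so it should not be read as a statement that Ki-67 readers are masked to outcome and nothing else. For Ki-67 the finding is an omission.

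**Some facts that a reader might infer are not stated.** One might suppose that the count is manual. That is natural, since image analysis is described for TSP-1 alone, but the plan only says that cells are counted. One might also suppose that the two slides are read weeks apart. Sections 2.0 and 9.0 say when tissue is obtained, not when it is stained or read, and batch reading is not ruled out. The point needs neither supposition: the plan permits separate, unmasked readings.

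**Masking to clinical outcome has some use.** The markers are also to be correlated with histopathological and MRI response, and patients are followed for up to 7 years. For some of those analyses, outcome masking helps. It does not help the primary endpoint.

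**The illustration does not model a reader nudging individual cases over 40%.** True. It applies one undercount to every post-treatment slide, which fits a stain shift or a general expectation about treated tissue. The gain from hiding the paired value alone is not quantified.

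**Core and excision slides may be recognisable.** This also stands, so coding may not fully hide the time point. It still hides whose slide it is and the paired value, and same-run staining works whether or not masking succeeds.

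**Conclusion.** The concern holds as a gap in how the primary endpoint is read. The plan gives no cell-selection, staining-run, coding or masking rule for Ki-67, and the single-arm comparison with a fixed 5% null cannot separate a reading shift from a drug effect.

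Its size is conditional. With 24 evaluable patients, the rule of at least 5 responders and no drug effect, a 10% undercount takes the false-positive rate from 0.4% to 5.5% at SD 0.3, leaves it below 1% at SD 0.25, and takes it from 8.7% to 31.3% at SD 0.4. Both the SD and the undercount are assumptions with no source in the documents.

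Three stronger conclusions are tempting and not supported. The first is that a positive result would be an artefact: nothing in the documents shows that a bias exists or how large it is. The second is that masking would bring the error under control in every case: at SD 0.4 or 0.5 the rate is already 8.7% or 30.4% without bias, which is a separate problem with the null. The third is that the same argument settles the MRI tumor outlines. Section 2.0 states no masking for those either, but the MRI parameters are secondary and analysed as changes in continuous measures, so the calculation here does not carry over.

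This is a worthwhile, inexpensive improvement that should be made before slides are read, because an unmasked reading cannot be undone by analysis.

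**What to change.** Add to the Ki-67 subsection of Section 2.0 that each patient's core and excision sections are stained in the same run, given random codes, mixed with other patients' slides, and read by the same pathologist without the paired reading or the stated time point. State there how the counted cells are to be selected. Apply the same handling to the exploratory immunohistochemistry markers in item 3. In Section 9.0, note that the baseline Ki-67 sample is taken before treatment but may be read later.

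The cost is slide coding and batch staining. No extra reader or tissue is needed, and the sample size does not change. Entry is unaffected: Section 5.0 requires ER or PR positivity and sets no Ki-67 criterion, so ER and PR can still be read at once. The drawbacks are that baseline Ki-67 is unavailable until the batch is read, and that the time point may still be guessed from the look of the specimen. Even then the paired value stays hidden, and between-run stain drift within a pair is removed.

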3.0 DRUG INFORMATION

Anastrozole:

a. DESCRIPTION

Anastrozole is a nonsteroidal aromatase inhibitor. Anastrozole is highly potent and specific for aromatase, and represents the fourth generation of aromatase inhibitors. Unlike aminoglutethimide, an early aromatase inhibitor, anastrozole does not inhibit adrenal steroid synthesis. Patients taking anastrozole, therefore, do not require glucocorticoid or mineralocorticoid replacement therapy. Anastrozole has a significant effect on suppression of serum estradiol levels, and it offers an alternative to tamoxifen in antagonizing estrogen. Anastrozole causes less weight gain than megestrol and may offer a survival advantage over megestrol in women with advanced breast carcinoma. Anastrozole was FDA-approved for the treatment of advanced breast cancer in postmenopausal women whose disease has progressed during tamoxifen therapy in December 1995. In September 2000, the FDA approved anastrozole for the first-line treatment of postmenopausal women with advanced or metastatic breast cancer. Mechanism of Action: Anastrozole inhibits aromatase, the enzyme that catalyzes the final step in estrogen production. Anastrozole is an oral, competitive, non-steroidal inhibitor of aromatase and is less likely to exhibit agonist or antagonist steroidal properties. The formation of adrenal corticosteroids or aldosterone is not affected by anastrozole; only serum estradiol concentrations are affected by anastrozole. In postmenopausal women, the principal source of circulating estrogens is from the conversion of adrenal and ovarian androgens (androstenedione and testosterone) to estrogens (estrone and estradiol) by aromatase in peripheral tissues. Inhibition of aromatase may result in a more complete estrogen block than surgical ablation. Extraglandular sites are more amenable to aromatase inhibition by anastrozole than are premenopausal ovaries. Inhibiting the biosynthesis of estrogens is one way to deprive the tumor of estrogens and to restrict tumor growth. Estradiol plasma concentrations decrease about 80% from the baseline with continued dosing of anastrozole. Aromatase inhibitors might also inhibit estrogen production at the tumor cell. However, tumor production of estradiol may be insignificant because aromatase activity appears to be low. Anastrozole has little or no effect on CNS, autonomic, or neuromuscular function.

b. TOXICOLOGY

Human Toxicity: Hot flashes (26.5%) are the most commonly reported adverse reaction to anastrozole during first-line therapy for breast cancer. In patients receiving anastrozole for progressive breast cancer, hot flashes occurred in 12.6% of patients. Vaginal irritation (i.e., dryness) and vaginal bleeding have also been reported with anastrozole. Vaginal bleeding occurs primarily during the first few weeks after changing from existing hormonal therapy to treatment with anastrozole. If bleeding persists, further evaluation should be considered. Tumor flare with associated bone pain has been reported during first-line anastrozole therapy for breast cancer.

GI adverse reactions occurred in up to one-third of patients receiving anastrozole. These reactions included, anorexia, constipation, abdominal pain, diarrhea, nausea/vomiting, and xerostomia (dry mouth). Weight gain has been reported in 2% of patients taking anastrozole, but occurs less frequently than with megestrol. Elevated hepatic enzymes, primarily serum gamma glutamyl transferase (GGT), have been observed in patients with liver metastases receiving anastrozole or megestrol. These changes were likely due to the progression of liver disease in these patients, but other contributing factors cannot be ruled out. Nervous system adverse reactions to anastrozole include anxiety, confusion, depression, dizziness, headache, hypertonia, insomnia, and paresthesias. Thromboembolism has been reported in patients treated with anastrozole (3.5%). The incidence of thrombosis is less than that reported with tamoxifen (6.5%) or megestrol (4.7%) during clinical trials. Specific cases included angina, cerebrovascular accident, cerebral ischemia, cerebral infarct, myocardial infarction, myocardial ischemia, pulmonary embolism, retinal vein thrombosis, and thrombophlebitis.

Other reported adverse events to anastrozole regardless of causality are arthralgia, asthenia, back pain, chest pain (unspecified), diaphoresis, dyspnea, fever, flu-syndrome, hypertension, increased cough, lethargy, pain (unspecified), myalgia, pelvic pain, peripheral edema, pharyngitis, pruritus, rash (unspecified), and vasodilation. Infections including bronchitis, rhinitis, sinusitis, and urinary tract infections have been reported in 2—5% of patients receiving anastrozole.

Drug Interactions: Anastrozole should not be given concurrently with any estrogens or estrogen-containing products, including oral contraceptives and some OTC hormonal preparations (e.g., prasterone or androsteindione, dehydroepiandrosterone, DHEA), as these could interfere with the pharmacologic action of anastrozole

c. PHARMACOLOGY

Kinetics: Anastrozole is well absorbed and distributed throughout the systemic circulation (85% bioavailability). Maximum plasma concentrations occur within 2 hours. Pharmacokinetics are linear, even with repeated dosing. Plasma concentrations approach steady-state levels by about the seventh day of once-daily dosing. Hepatic metabolism accounts for approximately 85% of elimination of anastrozole. Within 72 hours, about 60% of a dose is excreted in the urine as metabolites and only 10% as unchanged drug. Three metabolites have been identified in plasma and urine, and there are several unidentified minor metabolites. No pharmacological activity has been attributed to triazole, the main circulating metabolite. The other known metabolites are a glucuronide conjugate of hydroxy-anastrozole and a glucuronide conjugate of anastrozole. Although hepatic cirrhosis reduces apparent oral clearance of anastrozole, no dosage adjustments are needed because plasma concentrations remain within the same range as for patients without hepatic disease. Anastrozole has a terminal elimination half-life of about 50 hours. Renal clearance of anastrozole does decrease proportionally with creatinine clearance, but overall this has very little effect on total body clearance. No dosage adjustments are therefore necessary for patients with impaired renal function.

Formulation: Anastrozole is supplied in 1mg tablet

Administration of anastrozole: 1mg po once a day

Storage and stability: Store at controlled room temperature (59°F to 86°F [15°C to 30°C])

Supplier: Anastrozole is commercially available for purchase by the third party

Mechanism of Drug Destruction: Documentation indicating study drug was Destroyed will be sent to AstraZeneca.

